4 STUDY DESIGN

4.1 Study Overview

This is a single center, open label, parallel group trial comparing the efficacy of two different strengths of HFA flunisolide on lung function in asthma patients with small airway disease. We will enroll approximately 50 pediatric patients (ages 6-18, see discussion on sample size below) with mild to moderate asthma based upon the National Heart, Lung, and Blood Institute asthma guidelines.²¹ These patients will be recruited from new patients presenting to a pediatric pulmonary clinic as well as from general pediatric clinics associated with the University of Louisville, School of Medicine. Patients will have been steroid-naïve for at least four weeks. Prior to enrollment, patients will have demonstrated small airway disease based on pre-bronchodilator FEF_{25-75%} of less than 65% predicted.²² Patients will be randomized to receive flunisolide at either 80mcg twice a day or 160mcg twice a day with every other consecutive patient receiving alternating therapy (Figure 1). Prior to starting therapy, baseline IOS and spirometry pre and post bronchodilator (BD) will be obtained (Table 1). Patients will be randomized as described above and will be followed up at six weeks. At that point, repeat IOS and spirometry will be obtained again.

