7 STUDY TREATMENTS

7.1 Method of Assigning Subjects to Treatment Groups

We will use a block randomization scheme to promote balance at the end of the study. Block randomization ensures that after each block of individuals are enrolled in the study (n individuals in total); an equal number of individuals will be assigned to each group (n/2 individuals in each group). We will use random block sizes of 8-12. Data about grouping will be kept by study coordinator in a secure, locked location in the clinic. A password protected electronic database will also be created to store patient data in which will be kept on an encrypted, password protected computer.

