8.2 Clinical Assessments

8.2.1 Demographics

Demographic information (date of birth, gender, race, ethnicity) will be recorded at the Screening Visit.

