9.2 Visit 2 (Baseline) (Day 0)

Subjects who meet eligibility criteria at Visit 1 will be scheduled to return for Visit 2 no sooner than the next day but no later than 56 days following the Screening Visit. The following procedures will be completed:

1. Obtain standardized asthma control score from parent/legal guardian
2. Review current health status/medical history
3. Review concomitant medications
4. Obtain vital signs (temperature, heart rate, respiratory rate and blood pressure)

5. Measure oximetry
6. Measure height and weight
7. Perform abbreviated physical examination (Investigator)
8. Have patient perform IOS pre-bronchodilator
9. Have patient perform spirometry pre-bronchodilator
10. Have patient perform IOS post-bronchodilator
11. Have patient perform spirometry post-bronchodilator

If the subject meets all eligibility:

12. Randomize to flunisolide HFA 80mcg 1 puff BID or flunisolide HFA 80mcg 2 puffs BID
13. Dispense Study Drug and albuterol sulfate with holding chamber.
14. Review instructions for Study Drug administration
15. Schedule subject for Visit 3 (Week 6 ± 1 week)

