15 STATISTICAL METHODS AND CONSIDERATIONS

Prior to the analysis of the data, a detailed Statistical Analysis Plan (SAP) will be written describing all analyses that will be performed. The SAP will contain any modifications to the analysis plan described below.

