15.1 Analysis of Physiologic Effects (Lung Function)

The primary goal of the current study is to determine the effects of Aerospan on lung function in children with small airway obstruction. Participants recruited into this randomized parallel group study will be randomly assigned to either receive (1) 80 mcg of Aerospan twice a day or (2) 160 mcg of Aerospan twice a day, during the six-week study period. Outcomes will be measured at baseline and at six-week follow-up as described above.

First we will start with straightforward tests for differences among the two groups to test if our randomization scheme was successful. Analysis of Variance (ANOVA) techniques will be used to test for difference among continuous variables, while Kruskal-Wallis, Fischer's Exact Tests and Wilcoxon methods will be used to test for differences among categorical variables.

The primary endpoint will be changes in outcomes, over time, from baseline to six-week follow-up. The change in scores from baseline to six-week follow-up will initially be compared using paired t-tests and Chi-squared tests for trend. Repeated measurements will be analyzed using generalized linear mixed-effects regression modeling (GLMM) techniques. For continuous outcomes (e.g., FEV1, FEF 25-75%, Fres, X5, AX, R5-R20.) the identity link function and normal distribution will be used. For count data (e.g., use of Beta-agonists, episodes of

coughing, episodes of wheezing, etc.) the log link function and the Poisson distribution will be used. If we dichotomize outcomes (e.g., a Beta-agonist was used, coughing occurred, etc.) the logit link function and Bernoulli distribution will be used. Statistical analyses will be performed using SAS® Version 9.3 (SAS Institute Inc., Cary, NC).

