15.2 Sample Size

Based on our preliminary studies, we anticipate that 10% of all potential participants will not be eligible and/or willing to participant; and that 10% of the eligible/willing participants will be lost to follow-up. Therefore, we will recruit a total of n=50 individuals for the current study. This is a feasible sample size for the research team to recruit and enroll in the current study. Power calculations were based on the anticipated total sample size (n=40) that will be available for complete analysis.

We will develop separate mixed-effects general linear models for each of the continuous outcomes. From the anticipated sample size (n=40) the study has 86% power to detect a 10% main effect of each treatment for each outcome, our anticipated effect size given preliminary studies. When using count data the study has 94% power to detect a 10% decrease in the rate of outcomes (coughing, wheezing, etc.), our anticipated change in the rate. Using the dichotomized version of some outcomes, this study has 80% power to detect on odds ratio of 1.32 with a two sided $\alpha=0.05$ (n=40). Therefore, we have more than sufficient numbers of participants in each comparison group.

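### Allocation is described both as alternation and as random blocks, and section 15.1 compares the two doses by a within-arm test and an unspecified model

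*Combined protocol and SAP*

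**What the plan says.** **Allocation.** Section 4.1 says flunisolide will be given "at either 80mcg twice a day or 160mcg twice a day with every other consecutive patient receiving alternating therapy", and then calls this randomisation. Section 7.1 describes block randomisation: "We will use random block sizes of 8-12". Sections 7.2, 9.2 and 15.1 say only that patients are randomised. The synopsis, 4.1 and 7.2.1 make the trial open label.

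**Analysis.** Section 15.1 begins: "The change in scores from baseline to six-week follow-up will initially be compared using paired t-tests and Chi-squared tests for trend". It continues: "Repeated measurements will be analyzed using generalized linear mixed-effects regression modeling (GLMM) techniques". For continuous outcomes it gives the link and the distribution. It lists no fixed effects, no dose contrast and no covariate, and neither 15.2 nor the synopsis adds any. Section 15 defers detail: "Prior to the analysis of the data, a detailed Statistical Analysis Plan (SAP) will be written". The document contains no such separate plan.

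**Data available.** At Visit 2 (section 9.2) the list includes "Have patient perform spirometry pre-bronchodilator", and IOS likewise; 9.3 repeats both at week 6. Section 8.2.1 adds: "Demographic information (date of birth, gender, race, ethnicity) will be recorded at the Screening Visit". On size, 15.2 says: "Power calculations were based on the anticipated total sample size (n=40) that will be available for complete analysis".

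**Age limit.** The synopsis gives 21 years as the upper limit; 4.1 and 5.2.1 give 18.

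**The concern.** The objective is a dose-related difference, so everything rests on one between-arm contrast with about 20 patients per arm. Two things weaken it.

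First, sections 4.1 and 7.1 cannot both be followed. Under alternation, anyone who knows the last assignment knows the next. The protocol leaves room to act on that knowledge. Ability to comply and disqualifying physical findings are left to the site investigator (5.2), and Visit 2, where assignment occurs, may fall anywhere from 1 to 56 days after screening (8.1.2). Selection of this kind affects adjusted and unadjusted analyses alike.

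Second, the first test named does not address the objective. A paired t-test asks whether an arm changed from baseline. Both arms may change with no dose difference, and significance in one arm only is not evidence of one. A chi-squared test for trend does not fit continuous lung function either. The model that follows could supply the contrast, but the plan does not say which one, or whether baseline is used to sharpen it.

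**Working it through.** **1. The plan's own figures.** 50 x 0.9 x 0.9 = 40.5, so the 40 analysed is reproduced. The 86% power for a 10% effect cannot be reproduced, because no SD or correlation is given. Reading 10% as 10 points, with two-sided alpha 0.05 (stated only beside the odds ratio), 86% needs an SD of change of:
- 10.1 for a two-sample t-test, 20 per arm;
- 13.9 for a paired test in one arm of 20;
- 20.3 for a paired test in all 40.

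The document does not show which was meant.

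**2. Predictability of the next arm.**
- Alternation (4.1): every assignment after the first is known.
- Random blocks (7.1): suppose the guesser always picks the arm used less so far in the block. In a block of 2m of known size, the expected number right is m + 2^(2m-1)/C(2m,m) - 1/2. Equal arms imply sizes 8, 10 or 12.
  - Size 8: 4 + 128/70 - 0.5 = 5.33, or 66.6%.
  - Size 10: 5 + 512/252 - 0.5 = 6.53, or 65.3%.
  - Size 12: 6 + 2048/924 - 0.5 = 7.72, or 64.3%.
  - Sizes mixed and unknown, 40,000 simulated lists of 50: 64.7%.

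**3. What an unconstrained two-visit model estimates.** With dose, visit and dose-by-visit terms and complete pairs, the interaction is (mean week 6 - mean baseline at 160) - (mean week 6 - mean baseline at 80). That is the difference in mean change. Baseline is subtracted with a slope of 1 rather than an estimated slope.

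**4. Precision against baseline adjustment.** Take the same SD, s, at both visits, and let rho be the correlation of baseline with week 6. The documents give neither, so rho is assumed.
- Variance of change: 2s²(1 - rho).
- Variance of week 6 given baseline: s²(1 - rho²).
- Ratio: (1 + rho)/2.

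Estimating covariate slopes with N = 40 costs a factor of 37/36 = 1.028 for baseline alone, or 37/35 = 1.057 for baseline and age. Age is taken to add nothing. The unadjusted SE is sqrt(2/20) = 0.316 SD of change, so the 95% half-width is 2.024 x 0.316 = 0.640. The adjusted half-width is 2.028 x sqrt(0.1 x ratio), shown for baseline and age.

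| rho | Ratio, baseline only | Ratio, baseline and age | 40 / ratio (baseline and age) | Half-width (SD of change) |
|---|---|---|---|---|
| 0.5 | 0.771 | 0.793 | 50.5 | 0.571 |
| 0.7 | 0.874 | 0.899 | 44.5 | 0.608 |
| 0.9 | 0.976 | 1.004 | 39.8 | 0.643 |
| near 1 | 1.028 | 1.057 | 37.8 | n/a |

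Simulation gave 0.776, 0.875 and 0.974 for baseline only (4,000 runs), and 0.799, 0.893 and 1.009 for baseline and age (20,000 runs).

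**5. Unequal SDs.** Let rho = 0.8, with a week-6 SD 25% above the baseline SD. Variance of change: 1 + 1.5625 - 2 x 0.8 x 1.25 = 0.5625. Variance given baseline: 1.5625 x (1 - 0.64) = 0.5625. The ratio is 1.00 before the small-sample cost, so the gain is gone. A smaller week-6 SD would favour adjustment.

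**The case against.** **Section 7.1 is the dedicated allocation section and its scheme is sound; 4.1 may be a slip.** This stands in part. A reader might infer that patients were alternated and that the trial is not randomised. The documents do not show that. They show two incompatible instructions. The word randomised elsewhere does not settle the matter, because 4.1 applies it to alternation too.

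**Paired may be loose wording.** The synopsis makes clear that a between-arm comparison is intended. That is fair as to intent, but the test named does not carry it out.

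**The model is unspecified, and a later SAP is promised.** This also stands in part. A reader might infer that the plan rules out covariates; it is simply silent. A two-visit model that gives both arms a common baseline mean fits the text and is about as precise as baseline-adjusted regression. But the SAP need only precede the analysis, by which time open-label data may have been seen, and it cannot undo alternation already used.

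**The efficiency gain is small and assumed.** This stands. Under proper randomisation the difference in mean change is unbiased. At rho 0.7 the interval narrows by about 5% (0.640 to 0.608). A reader might also suppose that more is lost the better baseline predicts week 6. Against a change score the reverse holds: the loss is largest when prediction is weak.

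**Nothing shows that age would help.** This stands. If outcomes are percent predicted, as the entry criterion is, age is probably largely built in.

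**Allocation and covariates are separate matters.** They are. They appear together because both bear on the same dose contrast; neither is evidence for the other.

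**Conclusion.** The point holds in two parts.

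(a) The allocation conflict between 4.1 and 7.1 is certain from the text. Under alternation every arm after the first is known, against about 65% correct guesses under the random blocks. The size of any resulting bias cannot be derived, since the documents do not say how far patients selected on a known arm would differ.

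(b) The first test in 15.1 does not compare the doses, and the model after it is not defined. The defect in the named test is certain. The precision loss is conditional on an unconstrained dose-by-visit fit, complete pairs, 20 per arm, equal SDs and assumed correlations. Adjusting for baseline and an uninformative age term then gives a variance ratio of about 0.79 at rho 0.5, 0.90 at 0.7 and 1.00 at 0.9. The worst-case cost under equal SDs is about 6%, or about 3% for baseline alone.

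Both parts should be fixed. The allocation conflict weighs more, because it cannot be repaired afterwards.

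**What to change.** 1. **Section 4.1:** delete the clause on alternating consecutive patients and refer to 7.1, keeping its random blocks. If enrolment has begun, state which method was actually used.
2. **Section 15.1:** replace the paired t-test. For each lung-function and IOS outcome, make the primary dose comparison a linear regression of the week-6 pre-bronchodilator value on dose and the Visit 2 pre-bronchodilator value, reporting the dose difference with a 95% CI. A two-visit mixed model with a common baseline mean is an acceptable alternative. Age is an optional further covariate, mainly useful if outcomes are not percent predicted. In an unconstrained two-visit model it must enter as age-by-visit, since an age main effect leaves the dose-by-visit estimate unchanged for complete pairs.
3. **Synopsis (minor):** change the upper age limit from 21 to 18 to agree with 4.1 and 5.2.1.

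The cost is one deleted clause, one rewritten analysis sentence and one corrected number. No extra patients, visits or measurements are needed.

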4.3 Secondary Efficacy Endpoints

The number of protocol-defined asthma exacerbations requiring treatment with oral steroids between the two groups will be monitored. We will also track frequency of albuterol use for acute symptoms, number of emergency room visits and hospital admissions for acute asthma exacerbations between the two groups.

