7.2.2 Handling/Dispensing

Study Test Drug will be distributed by MEDA Pharmaceuticals to the clinic site. Albuterol sulfate (PROAIR HFA, TEVA Respiratory, Inc, Sellersville, PA) will be dispensed to each patient at the time of enrollment.

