7.4 Measures of Treatment Compliance

Parents of subjects will be asked to bring all used and unused Study Drug containers to each study visit. Albuterol use can be documented via changes in the counter.

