8.1.3 Interim Visits

Enrolled subjects will return at 6 weeks as detailed below.

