9.3 Visit 3 (Week 6 ± 3 days)

1. Obtain standardized asthma control score from parent/legal guardian.
2. Review current health status/medical history and adverse events
3. Review concomitant medications.
4. Obtain vital signs (temperature, resting heart rate, respiratory rate and blood pressure)
5. Measure oximetry
6. Measure height and weight
7. Perform abbreviated physical examination
8. Have patient perform IOS pre-bronchodilator
9. Have patient perform spirometry pre-bronchodilator
10. Have patient perform IOS post-bronchodilator
11. Have patient perform spirometry post-bronchodilator

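### Section 15.1 does not say how a single, possibly overdispersed albuterol count per child will be modelled; a plain Poisson fit, which the text permits, would understate its standard errors

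*Combined protocol and SAP*

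**What the plan says.** Section 4.3 lists rescue use among the secondary efficacy endpoints: "We will also track frequency of albuterol use for acute symptoms". Section 15.1, repeated in the synopsis, gives the model in three steps.

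- The framework is "Repeated measurements will be analyzed using generalized linear mixed-effects regression modeling (GLMM) techniques".
- For counts, with beta-agonist use as the first example, "the log link function and the Poisson distribution will be used".
- A yes/no version is left open by the words "If we dichotomize outcomes", with a logit link and no rule for when it applies.

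No random effect, dispersion parameter, negative binomial alternative, robust variance or time offset is named.

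The data come from the following arrangements. Under Section 7.2.2 the albuterol inhaler "will be dispensed to each patient at the time of enrollment", and item 13 of Section 9.2 places this at the Baseline visit. Section 7.4 adds: "Albuterol use can be documented via changes in the counter". Section 8.1.3 provides one return visit: "Enrolled subjects will return at 6 weeks as detailed below".

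**The concern.** The counter on the study-supplied inhaler produces one number per child and no pre-treatment number. A model introduced for repeated measurements therefore has nothing repeated to work on for this outcome. An analyst following Section 15.1 literally could fit an ordinary Poisson regression of the Visit 3 reading on arm.

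That model sets the variance of each child's count equal to its mean. This would be right only if all children in an arm shared one underlying rate and puffs arrived independently. It is a strong assumption for mild to moderate asthma across an age range of 6 to 18 years (Section 5.2.1; the synopsis says 21). If it fails, the Poisson standard error is too small and a dose difference in rescue use would be declared too often.

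**Working it through.** **Inputs.** From the documents: 40 children analysed (Section 15.2), equal allocation (Section 7.2), so 20 per arm; one albuterol reading per child (Sections 7.2.2, 7.4, 8.1.3); two-sided alpha 0.05, stated in Section 15.2 only for dichotomised outcomes and assumed here for counts. Not in the documents, so assumed over a range: the mean count μ and the variance-to-mean ratio φ. Where a between-child dispersion k is used, φ = 1 + kμ.

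**1. The plan's own count-data figure.** Section 15.2 states 94% power for a 10% fall in rate. For a log rate ratio with n per arm, SE² = (1/μ₁ + 1/μ₂ + 2k)/n and power = Φ(|ln 0.9|/SE − 1.96). With k = 0 and n = 20:

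| Mean per child | 10 | 20 | 40 | 117.5 |
|---|---|---|---|---|
| Power | 17.5% | 30.5% | 53.6% | 94% |

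No rate is given, so the 94% cannot be reproduced. As a two-sided comparison of arms it needs about 117 events per child in six weeks and almost no between-child variance. However large the mean, SE² cannot fall below 2k/20, so power cannot exceed 91.5% at k = 0.01 or 32% at k = 0.05. A before-and-after reading in 40 children needs about 59 events per period, but the study inhaler supplies no earlier period. The stated power therefore gives no sign that overdispersion was allowed for.

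**2. Type I error of a plain Poisson fit.** The true variance of the estimate is φ times the reported one. Under no effect the test statistic has standard deviation √φ, so the error is 2(1 − Φ(1.96/√φ)) and the standard error falls short by 1 − 1/√φ.

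| φ (assumed) | 1.96/√φ | Type I error | SE shortfall |
|---|---|---|---|
| 2 | 1.386 | 16.6% | 29% |
| 3 | 1.132 | 25.8% | 42% |
| 5 | 0.877 | 38.1% | 55% |

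Simulation with 20 per arm, negative binomial counts of mean 10 to 20 and follow-up uniform on 35 to 49 days gave 18%, 27–28% and 38–40%. Poisson with Pearson scaling and an offset gave 4.3–5.7%. At greater dispersion the plain fit is worse: 57.5% (μ = 20, k = 0.5), 68.5% (μ = 20, k = 1) and 66.5% (μ = 40, k = 0.5).

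**3. The same data with a child-level random intercept.** In those last three settings (400 runs each, no offset) a Poisson mixed model gave 5.2%, 4.5% and 5.8%. Its mean standard errors were close to the empirical standard deviations (0.245 against 0.240; 0.365 against 0.358; 0.245 against 0.250). The simulation error on a true 5% is √(0.05 × 0.95/400) = 1.1 percentage points.

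**4. Unequal follow-up.** The heading of Section 9.3 allows 6 weeks ± 3 days (39–45 days). Item 15 of Section 9.2 and the synopsis allow ± 1 week (35–49 days). These passages need reconciling. For uniform timing the coefficient of variation is 0.041 or 0.096. The Poisson standard error is then understated by a factor √(1 + CV²μ): 1.01–1.03 for the narrow window and 1.05–1.17 for the wide one, at means of 10 to 40. In simulation, adding an offset barely changed either model (plain Poisson 56.2%, 67.5%, 65.5%; mixed model 5.2%, 4.8%, 5.2%).

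**The case against.** The strongest reply is that Section 15.1 places the Poisson choice inside a mixed-effects framework, and such models contain random effects. With one count per child, a random intercept acts as an observation-level variance term. It can be estimated because the Poisson distribution fixes the variance at the mean. Step 3 confirms that it works. In the milder settings (mean 10–20, φ from 2 to 5), a random-intercept Poisson model without offset gave 3.5–7.0%, against 3.8–7.3% for negative binomial with offset. This stands, and it rules out the reading that the standard errors will be too small in any event. It does not settle the matter, because the framework is tied to repeated measurements and no random effect is named.

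A second reply is that a pre-treatment count might be taken by history: Section 15.1 says outcomes are measured at both visits, and Section 8.2.3 records the frequency of concomitant medication at Baseline. The documents do not exclude this. It would not rescue the stated model, though. With two counts per child, a random-intercept Poisson model leaves within-child overdispersion unabsorbed, and simulated type I error was about 16–26% at a within-child variance-to-mean ratio of 2 to 3.

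Third, Section 15 promises a detailed SAP before analysis. That gives a natural place for the correction. But the SAP is to hold modifications to the plan described, so unless modified, Poisson remains the plan.

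**Conclusion.** The point holds as a gap in specification with a conditional consequence. If the albuterol reading is analysed as plain Poisson, which the text allows, type I error is about 17%, 26% and 38% at φ = 2, 3 and 5. If a child-level random intercept is fitted, it stays near 5%. The size rests on assumed dispersion, since the documents give neither a mean nor a variance.

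Two stronger inferences are not supported. A reader might conclude that the missing offset is itself a serious flaw; under either visit window its effect is small, although partial follow-up after early withdrawal could enlarge it. A reader might also conclude that the optional yes/no version materially inflates false positives. If nearly every child uses albuterol, that version seldom rejects at all. With P(any use) = 1 − φ^(−μ/(φ−1)), the proportion is 99.6% at μ = 10, φ = 3, but 55–75% at μ = 2 with φ from 2 to 5, so its information content is unknown. What remains is that its use and status are undefined.

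Only secondary count outcomes are affected; the primary lung-function analysis is not.

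**What to change.** In Section 15.1, and in the SAP that Section 15 promises, state the following.

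- The Visit 3 albuterol counter reading is analysed by negative binomial regression, or by Poisson regression with Pearson-scaled or robust variance.
- Arm is the effect. The asthma control score already collected at Baseline (Section 9.2) is a covariate.
- Log(days from dispensing to reading) is the offset, as a minor refinement.
- The count analysis is the analysis of record, and any dichotomised version is only supportive.

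Naming one of these variance approaches removes the dependence on how the mixed-model sentence is read. The cost is analysis wording only: no extra visits, children or measurements. The downside is that intervals will be wider than under plain Poisson, which is their correct size.

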SAFETY MONITORING	As this is an FDA approved drug being used in approved populations at approved doses, the elements listed under "safety evaluations" as above will be tracked by the PIs but no formal data safety review board will be in place.
STATISTICS Primary Analysis Plan	The primary aim is to compare the average change in spirometric values (FEV1 and FEF _{25-75%}) and IOS values (R5, R5-R20, AX, Fres) from baseline to Week 6 from participants randomized flunisolide HFA 1 inhalation BID and to flunisolide HFA 2 inhalations BID. The change in scores from baseline to six-week follow-up will initially be compared using paired t-tests and Chi-squared tests for trend. Repeated measurements will be analyzed using generalized linear mixed-effects regression modeling (GLMM) techniques. For continuous outcomes (e.g., FEV1, FEF _{25-75%} , Fres, X5, AX, R5-R20.) the identity link function and normal distribution will be used. For count data (e.g., use of Beta-agonists, episodes of coughing, episodes of wheezing, etc.) the log link function and the Poisson distribution will be used. If we dichotomize outcomes (e.g., a Beta-agonist was used, coughing occurred, etc.) the logit link function and Bernoulli distribution will be used. Statistical analyses will be performed using SAS® Version 9.3 (SAS Institute Inc., Cary, NC).
Rationale for Number of Subjects	Based on our preliminary studies, we anticipate that 10% of all potential participants will not be eligible and/or willing to participant; and that 10% of the eligible/willing participants will be lost to follow-up. Therefore, we will recruit a total of n=50 individuals for the current study. This is a feasible sample size for the research team to recruit and enroll in the current study. Power calculations were based

on the anticipated total sample size (n=40) that will be available for complete analysis.

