1 BACKGROUND

Flunisolide HFA is an inhaled corticosteroid that is a reformulated version of the older CFC preparation. The CFC formulation was approved in 1981 and had been in use as an asthma controller since with good results.¹ The HFA formulation, which is in solution as opposed to suspension, has superior lung deposition when compared to its CFC counterpart (68% versus 20%).¹ Studies have demonstrated flunisolide HFA's effectiveness with regards to controlling airway inflammation and improving lung function^{2,3} while maintaining an excellent side effect profile, including no measurable effect on growth over one year.⁴ These attributes make it ideal for use in pediatric patients in whom growth suppression is a common concern. In addition, the current device used for delivery has a built-in spacer to ensure optimal lung deposition.

It is known that flunisolide HFA is uniformly distributed throughout all airways, with deposition approaching 68% and less drug being deposited in the oral cavity than larger molecule inhaled corticosteroids. Fluticasone, for example, has a larger particle size and results in about 20% lung deposition, mainly in the central airways. Despite this, there is little data that specifically examines the effect of flunisolide HFA on small airway parameters in children with asthma. We propose a randomized parallel study between flunisolide HFA 80 mcg twice a day and 160 mcg twice a day to determine the effect of each dose on spirometry and impulse oscillometry (IOS) parameters.

Based on the small molecule size and even lung deposition, we hypothesize that we will see a dose dependent significant improvement in small airway parameters (FEF 25-75%, AX, Fres, X5, R20-R5) with flunisolide. Secondary outcome measures will include clinical effects such as frequency of coughing and wheezing, number of short acting beta agonists used, oral steroid doses required, emergency department visits, and hospitalizations. If the results support our hypothesis this will address an important problem in the field and shift current clinical practice paradigms by a refinement in interventions. It may also provide the foundation for future studies to directly compare flunisolide to other coarse molecules inhaled corticosteroids.

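### Albuterol use is planned as a count, but an open option to recode it as used/not used usually loses power, allows a second test, and rests on a power figure that n=40 does not deliver

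*Combined protocol and SAP*

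**What the plan says.** Section 4.3 adds a reliever outcome to the secondary endpoints: "We will also track frequency of albuterol use for acute symptoms". The Background describes it as a number. Section 7.4 gives the source: "Albuterol use can be documented via changes in the counter". Under Section 6 each child receives one study albuterol inhaler and is told to use it rather than any other.

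Section 15.1 first treats the outcome as a count with a log link and Poisson distribution: "For count data (e.g., use of Beta-agonists, episodes of" coughing, and so on. The sentence after that offers the same variable in binary form: "If we dichotomize outcomes (e.g., a Beta-agonist was used, coughing occurred, etc.) the logit link function and Bernoulli distribution will be used". The synopsis repeats the option under its primary analysis plan: "If we dichotomize outcomes (e.g., a Beta-agonist was used, coughing occurred, etc".

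Section 15.2 and the synopsis rationale for sample size then claim power separately for the two forms. For counts the claim is 94% for a 10% lower rate. For binary outcomes, introduced by "Using the dichotomized version of some outcomes", it is 80% for an odds ratio of 1.32, two-sided 0.05, n=40. Section 15 promises a separate, detailed SAP before analysis.

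**The concern.** One variable has two permitted analyses. Nothing says when the binary form would be used, which result would stand if they differ, or which outcomes the power sentence covers.

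Three things are at stake:

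- **Power.** The binary form treats a child with one actuation like a child with forty. Unless use is rare, it discards most of the information in the counter.
- **Error rate.** If both forms are tested and either may be reported, the outcome has more than a 5% chance of a false positive.
- **Justification.** The binary option looks adequately powered only because of the 80% figure, so that figure has to be checked.

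**Working it through.** **1. The plan's 80% figure.** Inputs from 15.2 and 7.2: n=40 analysable, equal allocation (20 per arm), odds ratio 1.32, two-sided 0.05. The reference proportion is not given, so I used 0.1 to 0.7.

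- At reference 0.5, the second proportion is 1.32/2.32 = 0.569, a difference of 0.069.
- Standard error = √(0.5×0.5/20 + 0.569×0.431/20) = 0.157.
- Power ≈ Φ(0.069/0.157 − 1.96) = Φ(−1.52) ≈ 6%.
- Over references 0.1 to 0.7 the result is about 5% to 6%, or up to 7% if the wrong-direction tail is counted.
- For 80% power at reference 0.5, n per arm = [1.96√(2p̄(1−p̄)) + 0.842√(p₁(1−p₁)+p₂(1−p₂))]²/(p₂−p₁)² ≈ 821. The other references tried (0.1, 0.3, 0.7) need 923 to 2,034.
- With 20 per arm the odds ratio detectable at 80% power is about 6.3 (reference 0.3) to 8.5 (reference 0.5).

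The stated 80% returns (78% to 81%, references 0.4 to 0.6) only if each child supplies 42 independent daily yes/no records. No diary is described. The inhaler is dispensed at Visit 2, so the counter yields one change per child.

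**2. Count against yes/no.** Assumptions, none of them in the documents: 20 per arm, negative-binomial counts (shape 0.5, 1 or 2; a smaller shape means more variation between children), a true halving of use on the higher dose, two-sided 0.05. The count test is quasi-Poisson with 38 degrees of freedom. The binary test is chi-squared on any use. Simulated power, count / yes-no:

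| Mean actuations in six weeks | Shape 0.5 | Shape 1 | Shape 2 |
|---|---|---|---|
| 0.5 | 8% / 13% | 12% / 16% | 15% / 19% |
| 2 | 22% / 12% | 35% / 18% | 47% / 26% |
| 5 | 26% / 11% | 44% / 15% | 66% / 17% |
| 10 | 29% / 10% | 50% / 10% | 75% / 4% |
| 20 | 30% / 8% | 51% / 5% | 79% / 0% |
| 40 | 28% / 7% | 53% / 1% | 83% / 0% |

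With shape 1, the chance of any use at mean m is 1 − 1/(1+m). Means of 5 and 2.5 give 83% and 71%; means of 20 and 10 give 95% and 91%.

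**3. Testing both.** With no dose effect, the chance that the quasi-Poisson or the yes/no test is significant is about 5% to 10% over means 2 to 40. It is near 9% with shape 1 at means 2 and 5, and falls to about 5% at mean 40, where the binary test hardly ever rejects.

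**4. The named count model.** Under the same assumptions with no dose effect, a plain Poisson test rejects in about 16% (shape 2, mean 2) to 83% (shape 0.5, mean 40) of trials. Section 15.1 calls for a generalized linear mixed model but does not specify its random effects. Whether the planned model would absorb this variation is therefore unknown.

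**The case against.** The plan is not silent on the analysis: 4.3 says frequency and 15.1 lists the count model first, so the binary form is only conditional. The promised SAP could still close the choice. Both points stand. That SAP is not among the documents, however, and the power sentence shows that the binary form is a live option.

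A reader might infer that nearly every child will use the reliever, so that the yes/no outcome is almost constant and cannot show a dose effect. The documents do not support this. They give no albuterol rate, and 4.1 describes mild to moderate asthma. At mean 5 with shape 1, any use is 83% against 71%, which is not constant. At about 0.5 actuations the yes/no test does slightly better. The 94% power figure for counts would imply very high event rates, but its named examples are coughing and wheezing.

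A reader might also infer that the choice of form decides the conclusion. That is too strong: the adjusted count itself has only 22% to 53% power at shapes 0.5 and 1 for means of 2 or more. The power loss and the error inflation also partly offset each other, because inflation needs a binary result that still varies.

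Finally, moving to a single count analysis without handling overdispersion could do more harm than the option it removes. That is correct, and it shapes the remedy.

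**Conclusion.** The point holds in a limited form. Section 15.1 and the synopsis leave open an untriggered binary analysis of an outcome that the plan otherwise treats as a count. If mean use is about 2 or more actuations per child in six weeks, the binary form has clearly lower power in every setting examined. If use is near 0.5, it does not. Reporting whichever of two tests succeeds costs a modest 5% to 10% type I error.

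The power results rest on assumed rates, dispersion and a halving of use. The failure of the 80% claim rests on much less: with one yes/no result per child, n=40 gives about 5% to 7% power at an odds ratio of 1.32 for every reference proportion tried, and 80% needs more than 800 per arm.

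This is worth correcting before analysis. It affects a secondary outcome and leaves the primary lung-function conclusion untouched.

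**What to change.** - In 15.1 and the synopsis analysis plan, remove the option to dichotomize albuterol use.
- Name the counter change from Visit 2 to Visit 3 as the single tested version, compared once between the two doses. State that it stands for the use for acute symptoms named in 4.3, since a counter records every actuation.
- Specify a count model that allows overdispersion: negative binomial, quasi-Poisson or Poisson with robust variance.
- Report the proportion with any use by arm, without a test.
- Delete the dichotomized power sentence in both 15.2 and the synopsis. If binary analysis is kept for other outcomes such as coughing, restate it with the outcome, reference proportion and detectable odds ratio.

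The cost is a few sentences of text, with no change to data collection or sample size. The downside is that there is no formal logistic test for albuterol use. If use turns out to be very rare, that gives up a small power advantage.
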